3.1 Study Disease

Radiation dermatitis is an expected complication of radiotherapy that can lead to worse patient-reported quality of life during treatment and worse cosmesis, particularly in obese patients. Patients within the Bexar County Health System are more likely to have risk factors associated with radiation dermatitis, including obesity and diabetes. While our mostly low socioeconomic status patients stand to benefit the most from upfront therapy in order to prevent later cancer-related morbidity and mortality, they are also more likely to suffer from acute treatment-related morbidity, including radiation dermatitis.

Given the unmet medical need for therapies to address radiation dermatitis, our basic science team has been investigating candidate drugs to mitigate the problem. After screening a library of 130,000 compounds, we found that proton pump inhibitor (PPIs) have previously unrecognized yet potent effect in modulating inflammation and fibrosis induced by chemotherapy and ionizing radiation. Radiation-induced dermatitis occurs in most patients following radiotherapy. According to the NCI-CTCAE (Services, 2017) and RTOG (J. D. Cox, 1995) scoring systems, mild dermatitis (Grade I) is characterized by mild redness (erythema), epidermal thickening (hyperkeratosis) or dry desquamation and appears shortly after initiation of T. Moderate dermatitis (Grade II) occurs within two weeks of radiotherapy and manifests painful and intense erythema, loss of hair from the root (epilation), blisters and edema. Of note, the presence of grade II toxicity is generally regarded as clinically significant toxicity. In severe dermatitis (Grade III and IV), moist desquamation occurs excessively and may lead to persistent inflammation, full-thickness skin necrosis and severely painful ulceration that is prone to infection. The acute effects occur almost immediately at radiation doses between 2 and 40 Gray (2-40 Gy) whereas chronic effects occur several months-to-years after exposure to high radiation doses (> 45 Gy) and typical skin changes include atrophy, scarring and spider veins (telangiectasia) (S. R. Hymes, 2006).

The effect of radiation on the skin is in part due to its effect in promoting the production of highly reactive free radicals that are involved in DNA damage. In addition, radiation upregulates inflammatory cytokines (M. A. Brach, 1993) (e.g., $TNF\alpha$, $IL1\beta$, IL6, VCAM1 and ICAM1) that can exacerbate sustained injury and compromise skin integrity. Almost all head and neck cancer patients are profoundly affected by severe dermatitis (Grade II or higher) due to the development of serious skin reactions described above. The predictive risk factors for prolonged effect of severe dermatitis include age, sex, body mass index (BMI), site and volume of the body exposed to radiation, use of concurrent radiosensitizing drugs or chemotherapy regimen and presence of diabetes, autoimmune disorders, or genetic mutations (F. Meyer). Severe dermatitis can result in discontinuation of the radiotherapy before completion of the prescribed dose and threatens the relapse of underlying cancer (S. A. McCloskey, 2009), (Asa Bostrom, 2001).

Page 5 of 23

3.2 Rationale for Dermaprazole

Several non-pharmacological and pharmacological approaches have been evaluated for the prevention, treatment or management of severe radiation dermatitis (P. Okunieff). However, the use of many of these agents is not recommended either due to lack of efficacy or insufficient clinical data. Meanwhile, various pharmacological agents have been developed to mitigate radiation dermatitis. Of these, topical corticosteroids are the archetype. Among the steroid-based products, mometasone furoate (0.1%), betamethasone (0.1%) and hydrocortisone (1%) are extensively studied in clinical trials (Andrew Hindley, 2014).

While steroid use has been shown in clinical trials to decrease radiation dermatitis, some drawbacks have limited their widespread use including concern regarding: risk of cutaneous atrophy, stretch marks (striae), and secondary skin infection (e.g., cellulitis, candidiasis).

Proton pump inhibitors now have well described anti-inflammatory effects (R. R. Kedika, 2009). Our earlier research discovered that PPIs directly regulate the nitric oxide synthase (NOS) pathway via inhibition of the inducible isoform (iNOS) which is significantly expressed in skin cells in response to inflammatory stimuli as in radiation or chemotherapy. The nitric oxide (NO) catalyzed by iNOS is short-lived and rapidly oxidizes to peroxynitrite (OONO-); a highly reactive molecule that is involved in the generation of nitrotyrosine; a more stable product that is involved in tissue inflammation. Additionally, a number of inflammatory cytokines released during chemoRT are known to enhance NO production. We found that regulation of the iNOS pathway by PPIs is due to their direct interaction with dimethylarginine dimethylaminohydrolase (DDAH), an enzyme that breaks down asymmetric dimethylarginine (ADMA, the endogenous and competitive NOS inhibitor). Subsequently, we showed that esomeprazole is the most potent PPI that controls the pro-inflammatory enzyme DDAH and many classic pro-inflammatory cytokines (such as NFKB, TNFα, IL1β, IL6, VCAM1, and ICAM1) that are reported to be pathologically upregulated in radiation dermatitis.

Page 6 of 23

We recently reformulated esomeprazole powder into a Lipoderm®-based cream (Dermaprazole) that retained the inherent biologic antioxidant, anti-inflammatory, and antifibrotic effects of esomeprazole. This was executed by weighing of >98.5% purity esomeprazole powder and placing in a

[figure not shown]

Figure 1: Topical application of Dermaprazole Improves skin appearance in a model of radiation-induced dermal inflammation & fibrosis. Mice were irradiated (2 x 15 Gy) on Days 0 & 7. Dermaprazole, vehicle (base) cream, or the corticosteroid hydrocortisone were applied once a day on the indicated days (D1-D30 for prophylactic group & D10-D30 for therapeutic group). Representative images from the same animals are shown (n=10 animals/group).

mortar, wetting with propylene glycol, and mixing with a transdermal base (i.e., Lipoderm). Notably, our LC-MS study showed that a relatively low strength of Dermaprazole (1-2%) was highly stable and biologically active in modulating

esomeprazole target genes.

Accordingly, we evaluated the efficacy of this formulation in a mouse model of RD in a prophylactic and therapeutic settings in the presence of corticosteroid control. Remarkably, our study showed that while 90% of the animals in the

[figure not shown]

Figure 2: H&E stain showing that topical delivery of Dermaprazole improves skin histology in an animal model of radiation-induced dermal inflammation & fibrosis. Mice were irradiated (2 x 15 Gy) on Days 0 & 7. Dermaprazole, vehicle (base) cream, or the steroid hydrocortisone (1.0%) were applied once a day on the indicated days (D1-D30 for prophylactic group & D10-D30 for therapeutic group). Dermal thickening is observed in the Vehicle group and profound loss of skin integrity is seen by Day 30 in the steroid-treated group. Representative images are shown at 20X mag.

corticosteroid group had grade II or higher dermatitis, topical PPI mitigated the radiation dermatitis in most of the animals with only 20% showing grade II or higher radiation dermatitis (Figure 1). We also observed that Dermaprazole use led to significantly lower ulceration, necrosis, inflammation, and fibrosis (Figure 2 and Figure 3). Overall, most Dermaprazole treated animals showed complete or nearly complete closure of the

wounds within 4 weeks following exposure to ionizing radiation (Pham, et al., 2019).

[figure not shown]

Figure 3: Masson's trichrome stain showing that Dermaprazole inhibits skin fibrosis in an animal model of radiation-induced dermal inflammation & fibrosis. Dermaprazole, vehicle (base) cream, or the steroid hydrocortisone (1.0%) were applied once a day on the indicated days (D1-D30 for prophylactic group & D10-D30 for therapeutic group). Increased collagen deposition (blue stain) & dermal thickening are observed in the vehicle and steroid groups. Representative images are shown at 20X mag.

4	Patient Selection
	4.1 Inclusion Criteria
	a) Patients with head and neck malignancy (including radiation therapy to primary head cancers of any histology and/or neck lymphatics, excluding brain malignancies)
	b) Biopsy proven diagnosis of head and neck malignancy
	c) Planned to receive chemoradiation of at least 60Gy
	d) Age 18 years or older
	e) Eastern Cooperative Oncology Group (ECOG) performance status 0 - 2
	f) Written Informed Consent
	g) History and Physical within 12 weeks of enrollment
	h) Agree to not take proton pump inhibitors during treatment.
	4.2 Exclusion Criteria
	a) Prior head and neck radiotherapy
	b) Neoadjuvant chemotherapy
	c) Any serious medical condition or illness that would preclude the safe administration of the trial treatment including, but not limited to, active infection, symptomatic heart failure, unstable angina, psychiatric illness or social situations that would limit compliance with treatment
	d) Currently taking proton pump inhibitors. Eligible if discontinues with physician approval.
	e) Lack of concurrent chemotherapy
	f) Open wound at time of simulation
	g) Known autoimmune, connective tissue, or skin disorder; or other theoretical radiosensitivity to include bullous pemphigoid, dermatomyositis, lupus of the skin and scleroderma
	h) Pregnant or lactating patients
	i) Concurrent chemotherapy with cetux imab

Page 8 of 23

5 Treatment/intervention plan

5.1 Baseline and Screening Evaluations

- Informed consent
- Review of inclusion/exclusion criteria
- Comprehensive History and Physical Exam (within 12 weeks of registration)
- ECOG Performance Status
- Pregnancy test (for women of child-bearing potential)
- SkinDex16 questionnaire
- Photographic documentation of skin at baseline
- WBC, Hgb, ALT, AST, creatinine and calcium taken from standard care clinical labs drawn closest to consent
- Research Blood Draw to Central Labs: CRP, TNFa, IL-1b, IL-6

5.2 Randomization

Enrolled patients will be randomized in a 2:1 fashion to arm 1 (Dermaprazole) or arm 2 (Aquaphor). A randomization table will be generated by block randomization using a computer program (Sealed Envelope™). This table will be provided to the MCC Investigational Pharmacy prior to start of study enrollment. Each patient that has been enrolled into the study and consented will be allocated to arm 1 or arm 2 according to the sequence of the randomization table.

5.3 Radiotherapy Administration

Dose, Prescription, and Planning: Head and neck radiation of over 60Gy will be permitted with or without boost up to 70Gy (but not higher). Radiation is to be delivered 5 days per week (with exception of weeks with holidays), using intensity-modulated technique.

Simulation and Treatment: CT-based simulation with thermoplastic mask and volumetric planning must precede treatment. Tissue-equivalent bolus is permitted on protocol. Daily cone beam CT images are required to confirm accurate delivery.

Resimulation: Will be done in the last week of radiotherapy to allow for recalculation of beams.

5.4 Intervention

Head and neck radiation treatment will follow standard practice. Variations (dose adjustments, delays, etc) that follow standard clinical practice are allowed and are not considered deviations, though these will be recorded to assess for interference.

Patients will be managed with twice daily prophylactic use of the proposed intervention (Dermaprazole) topical cream for radiation dermatitis or Aquaphor. The amount of cream or Aquaphor will be 2cc per application and will be measured in pre-filled capped syringes for every application.

The Dermaprazole topical cream will be manufactured by Village Pharmacy in Houston. After the product is compounded it will be overnight shipped to the Mays Cancer Center Pharmacy in insulated shipping containers with temperature monitors. The cream will be

Page 9 of 23

stable for a minimum of 60 days in airtight containers under refrigerated conditions ($2^{\circ} - 8^{\circ}$ C) and is stable at controlled room temperature for at least 1 week. Room temperature is 20° C – 25° C (excursions permitted between 15°C and 30°C). A one to three week supply of the cream will be dispensed to the subject during study participation, with the exception that a 2 - 3 week supply will be provided at the time of CT Simulation (determined by the anticipated radiation start date). The same method will be used for the dispensing of the Aquaphor except that refrigeration will not be done in the pharmacy.

Patients will be instructed to apply the cream/Aquaphor along the area exposed to radiation from the day of simulation to two weeks after completion, correlating with the acute phase of radiation dermatitis. If the time from CT Simulation to start of radiation is greater than 2 weeks then the patient may be instructed to start the cream/Aquaphor 2 weeks prior to the anticipated start of radiation rather than at the time of CT Simulation. In the event of a delay from the time of CT simulation to the start of XRT, if the patient has no more than 3 days of interruption of the cream, this will not be considered a violation of the protocol. An interruption longer than 3 days will be considered a minor deviation. Patients who develop moist desquamation in the radiation treatment area may be prescribed a topical antibiotic or other standard of care treatment if indicated. Subjects will be instructed to not use other lotions, creams or any other products in the radiation treatment area without the study doctor's approval.

Neither the Dermaprazole cream or the Aquaphor is expected to be irritating or sensitizing but, subjects will be instructed to inform study personnel if a skin irritation occurs. If eye contact occurs the subject will be instructed to flush the eyes with water while open and to inform study personnel.

5.5 Assessments & Labs During Treatment

Weekly on-treatment assessments are as follows:

- Focused skin exam
- Adverse event/toxicity evaluation, including CTCAE version 5 evaluation of radiation dermatitis with note of components (erythema, epilation, fibrosis, etc)
- SkinDex16 questionnaire
- Photographic documentation of skin reaction with dermatologist's evaluation of CTCAE version 5 from this photography (photography may be discontinued if dermatitis radiation has resolved, or does not occur, at the discretion of the treating investigator or Principal Investigator)
- Compliance diary
- WBC, Hgb, ALT, AST, creatinine and calcium taken from standard care clinical labs
- Research Blood Draw to Central Lab: CRP, TNFa, IL-1b, IL-6 (in the last week of radiation and at 2 weeks after end of radiation)

Page 10 of 23

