2 OBJECTIVES

2.1 Safety/Efficacy

2.1.1 Primary Objective

A. Determine if objectively lower rates of significant radiation dermatitis occur with Dermaprazole for HNC patients receiving radiation when compared to patients receiving Aquaphor. An objective measure will be tabulated: the rate of clinically significant (CTCAE version 5 grade 2 or higher) radiation dermatitis. This measure will be reported weekly during treatment by both the treating radiation oncologist and blinded review by a board-certified dermatologist via medical photography.

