2.1.2 Secondary Objectives

2.2.2.1

To assess the highest grade of CTCAE version 5 radiation dermatitis during radiation treatment

2.2.2.2

To assess the time to occurrence of CTCAE version 5 grade 2 or higher acute radiation dermatitis.

2.2.2.3

To assess the time to healing if CTCAE version 5 grade 2 or higher acute radiation dermatitis develops.

2.2.2.4

To evaluate quality of life via acute and long-term symptoms and symptom scores utilizing the SkinDex16 scoring system.

2.2.2.5

To evaluate the threshold dose at which RD appears in either arm, utilizing skin dose tracking structures (V20 to V80 in 5 Gy increments reaching skin shell contours of "skin minus 3 millimeters" and "skin minus 5 millimeters")

2.2.2.6

To evaluate the threshold dose at which RD appears in either arm, using the same metrics as in 2.2.2.5, but with a new simulation scan in the last week of radiotherapy

2.2.2.7

To evaluate the effect of dermaprazole on inflammatory markers: CRP, TNFa, IL-1b, IL-6, by measuring values before, during, and after treatment. We expect this to give further evidence for the mechanism of action of dermaprazole.

Page 4 of 23

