7 MEASUREMENT OF EFFECT

Rates and severity of radiation-related toxicity will be defined using NCI Common Terminology Criteria for Adverse Events version 5. These will be used in assessment by the treating radiation oncologist as well as during blinded review by the dermatologist.

The following definitions will be used:

• Grade 1: Mild; asymptomatic or mild symptoms; clinical or diagnostic observations only; intervention not indicated

Page 13 of 23

- o Faint erythema or dry desquamation
- Grade 2: Moderate; minimal, local or noninvasive intervention indicated; limiting ageappropriate instrumental activities of daily living (ADL)
 - o Moderate to brisk erythema; patchy moist desquamation, mostly confined to skin folds and creases; moderate edema
- Grade 3: Severe or medically significant but not immediately life-threatening; hospitalization or prolongation of hospitalization indicated; disabling; limiting self-care ADL
 - Moist desquamation in areas other than skin folds and creases; bleeding induced by minor trauma or abrasion
- Grade 4: Life-threatening consequences; urgent intervention indicated.
 - O Skin necrosis or ulceration of full thickness dermis; spontaneous bleeding from involved site; skin graft indicated
- Grade 5: Death related to adverse event.

Compliance to intervention and use of other topical agents will be documented qualitatively during weekly assessments. Patient's effect on quality of life will be evaluated using SkinDex 16 (Appendix 1).

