For purposes of this study, an adverse event is considered expected when the events are those related to systems within the radiation treatment field and include: infection, allergy, or short & long-term (greater than 6 month) skin changes.

Radiation: The common side effects of radiation to the head and neck most commonly includes radiation dermatitis (i.e., erythema, blistering, pigmentation changes) and fibrosis/firmness of head and neck in the long-term. Commonly, patients develop dry mouth, changes in taste, pain when swallowing, and weight loss. Long term, some patients can continue to have changes in taste and lymphedema.

Dermaprazole: The interventional cream is not yet tested in humans and reactions *in* vivo (especially in patients experiencing radiation dermatitis) are not yet known. Possible side effects include allergy or infection. Given the success in pre-clinical studies, it is unlikely that the interventional cream would lead to worsened rates of radiation dermatitis and skin integrity, though this is a possibility.

Acute and late designations will be defined by the timing of occurrence from treatment.

- Acute toxicity will be defined as events occurring during or within 90 days of treatment completion.
- Late toxicity will be defined as events occurring or persisting ≥90 days from treatment completion.

Attribution: An attribution scale which will be utilized to attribute relatedness of the adverse event to the radiation treatment or to the Dermaprazole/Aquaphor as determined by the treating investigator or Principal Investigator. Assignment of attribution is the responsibility of the treating investigator or Principal Investigator.

Page 19 of 23

- Definite The AE is clearly related to the study treatment.
- Probable The AE is likely related to the study treatment.
- Possible The AE may be related to the study treatment.
- Unlikely The AE is doubtfully related to the study treatment.
- Unrelated The AE is clearly NOT related to the study treatment.

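### Section 5.5 lets an investigator for whom no masking is described stop the weekly photographs during radiation, which can end the blinded half of the primary dermatitis measure and conflicts with section 2.1.1 and the calendar

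*Combined protocol and SAP*

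**What the plan says.** Section 2.1.1 defines the primary measure as "the rate of clinically significant (CTCAE version 5 grade 2 or higher) radiation dermatitis" and gives it two sources: "This measure will be reported weekly during treatment by both the treating radiation oncologist and blinded review by a board-certified dermatologist via medical photography". Section 7 repeats the pairing and applies the word blinded only to the dermatologist.

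Section 5.5 lists the weekly on-treatment assessments. Its photography item, which includes the dermatologist's grade, carries a parenthesis: "photography may be discontinued if dermatitis radiation has resolved, or does not occur, at the discretion of the treating investigator or Principal Investigator". It names no earliest week, no minimum dose and no end-of-radiation condition, and the dermatologist has no part in the decision.

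The calendar in section 6.1 marks both photography and the blinded grade in every week from 1 to 7. Its photography footnote (d) covers the camera, file storage and de-identification, and has no stopping option. Sections 5.6 and 6.1 schedule photographs with dermatologist grading again at Month 1, Month 3 and later, also with no stopping option.

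The oncologist's weekly skin examination and CTCAE grade have no stopping option anywhere. Section 8.4 admits to the analysis patients who complete at least 60 Gy and the 30-day follow-up. No section says how a week without a photograph is counted, or which assessor's grade decides the primary comparison.

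**The concern.** The dermatologist sees photographs and nothing else, so a decision to stop photographing is a decision to stop blinded measurement. Section 5.5 gives that decision to the treating investigator or Principal Investigator and bases it on that person's own reading of the outcome. Whether a patient is observed blind in later weeks can therefore depend on an earlier judgement made without described masking, which is what blinded review is there to avoid.

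The second trigger cannot be established while treatment is under way. That dermatitis has not occurred is known only once radiation and the acute period are over. Eligible patients are planned for at least 60 Gy, and the secondary objectives in section 2.1.2 treat onset as something that varies with time and dose ("To assess the time to occurrence of CTCAE version 5 grade 2 or higher acute radiation dermatitis"; "To evaluate the threshold dose at which RD appears in either arm"). The other trigger carries a smaller version of the same risk: a mild reaction that has resolved may be followed by a grade 2 reaction.

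At stake are the blinded grade 2 or higher rate, the blinded highest grade and the blinded time to onset. With 30 and 15 patients, one missed event moves the observed rate by 1/30 = 3.3 points in the Dermaprazole arm or 1/15 = 6.7 points in the Aquaphor arm.

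**Working it through.** **1. The passages side by side.**

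| Place | Photographs and blinded grade during radiation |
|---|---|
| 2.1.1 | Weekly, no exception |
| 5.5 | Weekly, but may be stopped at investigator discretion |
| 6.1 calendar | Every week 1 to 7, footnote (d) without a stopping option |

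The three cannot all be followed.

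**2. What is lost if photography stops.** The oncologist's weekly grade continues and Month 1 is photographed. The exposure is therefore a grade 2 or higher reaction that first appears after the stop and is no longer at that grade at Month 1, together with the blinded onset time and peak grade of any reaction in that interval.

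**3. The plan's own sample size.** Inputs from sections 5.2, 8.2 and 8.3: 65% (Aquaphor) v 20% (Dermaprazole), alpha 0.05 two-sided, power 80%, allocation 2:1. The pooled rate is (0.65 + 2 × 0.20)/3 = 0.35. For the Aquaphor arm, without continuity correction:

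n = [1.960 × √(0.35 × 0.65 × 1.5) + 0.842 × √(0.65 × 0.35 + 0.20 × 0.80/2)]² / 0.45² = 12.8, rounded up to 13.

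The total is 13 + 26 = 39, as stated. At the planned 15 v 30, exact enumeration of all 2×2 tables with the uncorrected two-sided chi-square test gives power 0.863 at 65% v 20%, and type I error 0.051 at 65% in both arms.

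**4. Effect of missed events.** The documents do not give the share of blinded events that would be missed, so 10% to 30% is an assumption. Two further assumptions are that the blinded grade is the one analysed and that an unseen event counts as a non-event. With a share m missed, an arm's observed rate is p × (1 − m).

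*No true difference (65% in both arms), events missed in the Dermaprazole arm only:*

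| m | Observed Dermaprazole rate | Type I error |
|---|---|---|
| 0 | 65% | 0.051 |
| 10% | 58.5% | 0.066 |
| 20% | 52% | 0.121 |
| 30% | 45.5% | 0.221 |

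At 65% the arm of 30 would have 30 × 0.65 = 19.5 events, so 20% missed is about 4 patients.

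*Design alternative (65% v 20%), same share missed in both arms:*

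| m | Observed rates | Power |
|---|---|---|
| 0 | 65% v 20% | 0.863 |
| 10% | 58.5% v 18% | 0.802 |
| 20% | 52% v 16% | 0.730 |
| 30% | 45.5% v 14% | 0.646 |

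*Design alternative, events missed in the Aquaphor arm only:* power is 0.751, 0.607 and 0.447 at 10%, 20% and 30%. The bias can therefore run against the cream as well as for it.

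**The case against.** The best defence is that the clause is permissive, affects one of two assessors, and leaves much in place. The oncologist grades every week, so a reaction that appears after photography stops is still recorded in one of the two reports of the primary measure. Nothing bars restarting photographs. Section 5.7 continues them for in-field adverse events until resolution, although it sits under early discontinuation and does not reach a patient judged clear. Section 8.3 describes the main intention as understanding safety and tolerability. All of this stands and limits the loss to the blinded component. It does not remove the point: the component at risk is the only one described as blinded, and section 2.1.1 makes the comparison between arms the primary objective.

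The timing argument is also open to challenge. Section 3.1 places grade II within two weeks of radiotherapy and says almost all head and neck patients reach grade II or higher, which would make late first onset uncommon. The threshold-dose and time-to-occurrence objectives point the other way. The documents are mixed, and section 5.5 does not require even a two-week wait.

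A reader might go further and infer that investigators who know the arm will stop photographs selectively in the Dermaprazole group and create a false benefit. The documents do not support that. Knowledge of arm is a reasonable inference: only the dermatologist is called blinded, no masking of cream against Aquaphor is described, and the investigator judges "relatedness of the adverse event to the radiation treatment or to the Dermaprazole/Aquaphor as determined by the treating investigator or Principal Investigator". No section states it, however, and nothing shows in which direction the discretion would be used. Nor do the documents say that an unphotographed week becomes a non-event; they are silent.

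**Conclusion.** The point holds as an internal conflict with a real, bounded consequence, and should be fixed. Section 5.5 permits blinded grading to end during radiation on an outcome-based judgement by a person for whom no masking is described, while section 2.1.1 and the calendar require it every week. The loss is confined to blinded grade 2 or higher events, peak grade and onset time between the stop and Month 1.

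How often the clause would be used, and whether use would differ by arm, cannot be told from the documents. The calculated ranges (type I error up to 0.221, power down to 0.646) rest on the assumed 10% to 30% missed, on the blinded grade being analysed, and on unseen events counting as absent. The low end is modest: 10% missed in one arm moves type I error only from 0.051 to 0.066. Loss of power needs no difference between arms in how the clause is applied.

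**What to change.** Delete the parenthesis in section 5.5, so that it agrees with section 2.1.1 and the calendar. State that photographs and the dermatologist's grade are obtained in every radiation week in both arms, whatever grade the treating investigator assigns. Keep the Month 1 and Month 3 photographs already scheduled, and if a stopping option is wanted, allow it only after Month 3.

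In section 8, state that a week without a photograph is missing for the blinded grade and is not counted as grade 0 or 1, and that missed photographs will be reported by arm.

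The cost is a short amendment and a few more photographs and reads for patients with clear skin, at visits that already take place with the camera and reader already in the plan. Blinded grades that were never photographed cannot be recovered at analysis.
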